### **8.7.2. Blinding**

Only the research pharmacist will know the identity of the investigational product. The research pharmacist will keep the randomized assignment of subjects in a secure location. All other study staff will be blinded to treatment given. The site investigator or designated, approved study physician will make the decision to un-blind the identity of the investigational product if the study blind needs to be broken to make medical decisions regarding subject treatment. If it is determined that unblinding is necessary to assess AEs or SAEs for expedited reporting, the sponsor may decide to request unblinding of a subject.

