## **8.13. Subject and Study Discontinuation and Stopping Criteria**

### **8.13.1. Discontinuation of Individual Subjects**

Each subject has the right to withdraw from the study at any time. In addition, the investigator may discontinue a subject from the study at any time if the investigator considers it necessary for any reason, including the occurrence of an AE or noncompliance with the protocol. Subjects who withdraw from the study will not be replaced unless it is mutually agreed upon, in writing, between the investigator and the sponsor.

Some specific considerations for replacement of subjects include:

1. If a subject is considered eligible for the study but does not receive any investigational product, another subject will be enrolled to ensure that each cohort has the target number of subjects.
2. If a subject is randomized to the active group but withdraws from the study before the Day 3 clinic release procedures are performed, then a replacement subject may be considered.
3. If a subject for some reason is missing safety measures such as clinical laboratory assessments, vital signs, or FOBT.
4. If a subject for some reason is missing blood samples for PK measurements such that PK cannot be determined.

If a subject withdraws or is discontinued from the study, the reason(s) for the discontinuation from the study will be recorded and a physical examination, body weight, vital signs measurement, ECG, laboratory analyses, Stool Consistency Questionnaire, GI Symptoms Checklist, and AEs will be performed as soon as possible after discontinuation from the study. Additional blood samples for drug measurement may be collected at the time of discontinuation from subjects who are discontinued due to AEs; the clock time, and date the sample was taken will be recorded.

If a subject is discontinued from the study with an ongoing AE or an unresolved laboratory result that is significantly outside of the reference range, the investigator will attempt to provide follow-up until a satisfactory clinical resolution of the laboratory result or AE is achieved.

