8 PROCEDURE FOR UNBLINDING DATA

This study is a double-blind study. If the treatment assignment for an individual subject needs to be unblinded during the trial, the PI will contact the unblinded sponsor or data management center staff for the treatment assignment. A note to the file will be prepared by the person who performed the unblinding to indicate when the subject was unblinded, why the subject was unblinded, and to whom the unblinding information was given.

Blinding and unblinding procedures will be performed in accordance with Fast-Track's SOPs CT017 Procedures for Unblinding Investigational Agent Identity for a Study or a Single Subject, CT024 Preparation of Randomization Codes and Maintenance of Treatment Assignment Schedules, CT033 Security and Access to Clinical Trial Databases, and CT045 Development of Clinical Data Management Plans.

At the completion of the study, after the database has undergone edit checking and QA audit and is deemed ready to be locked, the treatment assignments will be uploaded to the main study database, and the database will be locked.

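### Replacement rule 2 in Section 8.13.1 depends on the treatment arm, so using it tells the blinded investigator that the withdrawn subject was on active drug

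*Protocol*

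**What the plan says.** Protocol Section 8.13.1 sets a default and names who may depart from it: "Subjects who withdraw from the study will not be replaced unless it is mutually agreed upon, in writing, between the investigator and the sponsor". It then lists four considerations for replacement. The condition of the second reads "If a subject is randomized to the active group but withdraws from the study before the Day 3 clinic release procedures are performed". What follows from it is permissive, not mandatory: "then a replacement subject may be considered". It is the only one of the four that names an arm.

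Protocol Section 8.7.2 says "Only the research pharmacist will know the identity of the investigational product" and "All other study staff will be blinded to treatment given". It gives two reasons to break the blind. The site investigator or an approved study physician may do so "if the study blind needs to be broken to make medical decisions regarding subject treatment". If assessment of AEs or SAEs for expedited reporting requires it, "the sponsor may decide to request unblinding of a subject". Replacement is not among these reasons.

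SAP Section 8 describes the unblinding of an individual subject differently: "the PI will contact the unblinded sponsor or data management center staff for the treatment assignment".

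**The concern.** Rule 2 can be applied only by someone who knows the arm. The investigator, one of the two parties who must agree to the replacement, is blinded under Section 8.7.2. Neither document routes the arm question through the pharmacist or any other unblinded person. Agreeing to a replacement on this ground therefore tells the investigator that the subject received kindolor tosylate.

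What is at stake is blinded severity grading. Under Section 11.1.3 the investigator assesses the severity of every AE. Severity enters stopping criterion b(ii) (two or more active subjects with moderate AEs in the same SOC) and b(iii) (one severe AE in an active subject). Section 8.13.2 defines the MTD, part of the primary objective, from those criteria. With thresholds this low, a single grade can decide escalation.

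Grading need not be complete when replacement is discussed. Section 8.13.1 calls for AE assessment after discontinuation and follow-up of ongoing AEs. Section 11.1.8 follows unresolved AEs for at least 7 days after the final visit, with exceptions.

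**Working it through.** **Why replacement would be wanted.** The plan's only design figure (Protocol Section 12.4, SAP Section 7) is the chance of seeing at least one AE among n active subjects, 1 − (1 − p)^n.

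- With n = 6 and p = 10%, 15%, 20%, 25%, this gives 46.9%, 62.3%, 73.8%, 82.2%. The stated 47%, 62%, 74%, 82% are reproduced.
- With n = 5 (one active withdrawal left out and not replaced), it gives 41.0%, 55.6%, 67.2%, 76.3%.

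The second line applies only if the withdrawn subject contributes no AE information. It shows why there is a reason to use rule 2; it is not an error in the plan.

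**What a rule 2 replacement discloses.** The inputs are the sentinel pair of one active and one placebo (Section 5) and the 5:1 allocation of the remaining six (Section 8.7.1). Before any disclosure, the probability that a given subject is on active is:

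- sentinel: 1/2 = 50%
- one of the remaining six: 5/6 = 83.3%

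After a replacement agreed on rule 2, it is 100% for the withdrawn subject. The effect on the other subjects is:

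- Sentinel pair: the partner goes from 50% to 0/1 = 0%, and so is identified as placebo.
- Remaining six: each of the other five goes from 5/6 = 83.3% to 4/5 = 80%, a small change.

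**Who holds the code, side by side.**

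- Section 8.13.1: the decision belongs to the investigator and the sponsor, and the condition is the randomized arm.
- Section 8.7.2: the pharmacist knows the arm, the investigator does not, and the permitted reasons to unblind do not include this decision.
- Section 10: an unblinded CRO statistician exists, but the stated task is to prepare tables and listings for the DSMB.
- SAP Section 8: some sponsor or data management staff are described as unblinded, which does not fit Section 8.7.2.

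The first two cannot both be followed when rule 2 is the ground used. The last two do not change this for the investigator, who must still agree.

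**The case against.** The strongest reply is that the leak is optional and often avoidable. Rule 2 is permissive, the list is introduced as some considerations only, and the default is no replacement. Rule 3, on missing safety measures, is arm-neutral. A subject who leaves before Day 3 release will often lack the Day 3 FOBT, and neither the early-termination column of the schedule nor the discontinuation assessments in Section 8.13.1 include one. Rule 3 could therefore support replacement in many of the same cases on blinded grounds, although its sentence is incomplete and states no consequence. This stands. A replacement alone does not reveal the arm; it does so when rule 2 is the ground used.

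A second reply is that the pharmacist could apply the condition privately. That is a sensible remedy, but Section 8.13.1 does not say it.

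A third is that the triggering AE will usually have been recorded before replacement is discussed, and that laboratory grades follow a published scale. This narrows the exposure. It does not remove it, because AEs can still be followed and graded after withdrawal.

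A fourth is that preferring to replace active subjects is a coherent choice: no hypotheses are tested, placebo is pooled, and the precision rationale rests on six active subjects per dose. This is accepted. The difficulty is who applies the arm condition, not the preference itself.

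A reader might also infer more than the documents support:

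- That rule 4 (PK cannot be determined) leaks the arm. As written it applies to any subject.
- That a withdrawn subject who is not replaced must be on placebo, which would identify the other five of the six as active. That needs routine replacement of active withdrawals, and the default is the opposite.
- That relatedness judgments drive the stopping criteria. Section 8.13.2 has no relatedness condition.
- That early withdrawals will mostly be subjects with AEs. AEs are named as one possible reason for discontinuation, but no withdrawal rate or breakdown of reasons is given.

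**Conclusion.** Rule 2 as written conflicts with Section 8.7.2. Each time it is the ground used, a blinded investigator learns that the withdrawn subject was on active (50% or 83% to 100%). For a sentinel, the investigator also learns that the partner was on placebo. This can happen while AE severity relevant to b(ii), b(iii) and the MTD is still being assessed.

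The conclusion rests on three assumptions: the pair and the six are allocated exactly 1:1 and 5:1; the investigator knows which rule is being applied; and no separate blinded procedure exists outside these documents. How often it would occur cannot be estimated from what is given.

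The conclusion is firm for the investigator and weaker for the sponsor. Section 8.7.2 implies that the sponsor is blinded by default, but SAP Section 8 refers to unblinded sponsor staff. A reader might infer that both parties are newly unblinded; the documents do not settle that.

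No sample-size or analysis figure changes. The point should be corrected, but it does not threaten the design.

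**What to change.** Reword rule 2 without reference to arm: any dosed subject who withdraws before the Day 3 release procedures may be considered for replacement. The investigator and the sponsor decide on blinded information. The research pharmacist then assigns the replacement to the arm of the subject replaced and does not disclose it.

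If replacement is to stay limited to active subjects, name an unblinded person outside the assessing team, such as the pharmacist or the unblinded statistician, to apply the arm condition. That process must also keep the arm from the investigator, since a replacement known to be limited to active subjects discloses it.

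Reconcile SAP Section 8 with Protocol Section 8.7.2 on who holds the code and whether any sponsor staff are unblinded.

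Nothing is needed on the Safety population: Section 12.2 already includes every subject who received a dose, so a withdrawn dosed subject stays in.

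The cost is one or two sentences in Section 8.13.1, one alignment between the documents and, under the arm-neutral wording, an occasional extra placebo subject.

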Eligible subjects will undergo intake procedures at the UCSD Clinical and Translational Research Institute Phase I unit on Study Day -1 (the day before starting dosing) and will complete final screening and baseline evaluations. On Study Day 1, subjects will receive the study drug after an overnight fast (about 8 hours) with no food allowed until 4 hours after dosing. Study drug tablets will be administered with 240 mL of water. Water will be allowed anytime except for one hour before and after dosing. Subjects will remain in the unit for at least an additional 48-hours for safety assessments and blood collections to determine plasma levels of kindolor. Pre-dose assessments will be conducted prior to administration of study drug on Study Day 1. Blood for PK analysis will be collected ~ 15 minutes prior to dosing, then at 0.25, 0.5, 1, 1.5, 2, 4, 8, 12, 24, and 48 hours after dosing. Safety will be assessed by collecting adverse events (AEs), vital signs, physical examination, ECG, FOBT, Stool Consistency Questionnaire, GI Signs and Symptoms Checklist, urine output (24 hours) and clinical laboratory tests (amylase, lipase, chemistry, hematology, coagulation tests, pregnancy tests, and urinalysis). AEs will be assessed daily after the start of dosing, with closer evaluations in the 4-hour period after the start of dosing. Sitting (3 minutes) vital signs will be taken during screening, at clinic check in, pre-dose, then at 15, 30, 60 minutes and 2, 4, 6, 12, 24, and 48 hours post dose. A 12-lead ECG will be obtained prior to dosing, then at 2, 6, 12, 24, and 48 hours post dose. When vital signs or ECG are scheduled at the same time as a PK blood draw, these assessments will be performed before drawing any blood. The FOBT will be performed at screening, clinic intake on Day -1, pre-discharge on Day 3, and at follow-up on Day 7. Subjects will return for a final follow-up visit 7 ± 2 days after discharge for a final safety assessment including ECG, vital signs, AEs, FOBT Stool Consistency Questionnaire, GI Symptoms Checklist, and clinical laboratory tests. Males will be contacted 90 days and females 28 days after study drug administration to verify continued contraceptive use and having not donated sperm for males and have not breast fed a baby or donated ova for females during this period. The study schedule of visits and assessments is shown in [Table 6](#).

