## **8.10. Early Termination Visit**

If the subject requests to withdraw from the study early, early termination assessments will be scheduled if the subject agrees, and the assessments in [Table 6](#) will be performed.

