### **8.13.2. Dose Continuation, Dose Escalation and Study Stopping Criteria**

Continuation of dosing within a cohort, or dose escalation to sequential cohorts will stop when either:

- a) The highest dose is reached or,
- b) Clinical/laboratory/AE findings meet any of the following stopping criteria:
  - i. Two or more subjects on active medication have clinical laboratory values meeting the criteria of moderate (Grade 2) intensity
  - ii. Two or more subjects on active medication experience moderate AEs of the same type (within the same MedDRA SOC)
  - iii. One or more subjects on active medication experiences any clinical laboratory value meeting the criteria of severe (Grade 3 or 4) intensity or an AE is determined to be severe in intensity
  - iiii. Any subject has a positive FOBT
- c) The mean kindolor systemic exposure levels exceed  $AUC(T_{last})=87,550$  ng.h/mL or  $C_{max} > 13,490$  ng/mL in a single subject in a cohort.
- d) The DSMB recommends stopping escalation after review of all the data from each cohort.

The maximum tolerated dose (MTD) will be considered the highest dose where no active medication subjects meet the study stopping criteria.

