#### **11.1.5. Gastrointestinal Adverse Events**

Gastrointestinal (GI) AEs will be assessed as follows:

- Stool Consistency Questionnaire – subject completed questionnaire ([Appendix A](#))
- GI Signs and Symptoms Checklist ([Appendix B](#))
- FOBT
- Open ended questions about AEs that are indicative of gastritis
- Clinical laboratory tests (hematocrit, hemoglobin, blood urea nitrogen (BUN), creatinine, ALT, and AST)
- Endoscopy (if indicated)

A-subject completed Stool Consistency Questionnaire ([Appendix A](#)) that asks 4 questions about GI symptoms will be utilized to assess GI AEs. The responses to the questions are based on a 4-point scale with 0 being no symptom and 3 being a severe symptom. The development of a new symptom or worsening of an existing symptom will be reported as an AE.

In addition, if a subject reports of any of the signs and symptoms of gastritis or potential GI ulcer complications or has a laboratory test result indicative of blood loss as shown in the GI Signs and Symptoms Checklist ([Appendix B](#)), the study gastroenterologist sub-investigator will do a thorough evaluation of the event and perform an endoscopy if it is considered warranted. A signs and symptoms checklist will be reviewed each day starting with Day 1, and then on Days 2, 3, and 7. Presence or absence of each sign or symptom will be recorded and if appropriate, a severity assessment or clinical significance evaluation will be performed.

Clinically significant changes in hematocrit and hemoglobin are defined as decreases of at least 10 percentage points and 2 g/dL, respectively. Clinically significant changes in other clinical laboratory tests will be defined as blood urea nitrogen  $\geq 40$  mg/dL, creatinine  $\geq 1.8$  mg/dL, ALT

and AST  $\geq 3$  times the upper limit of normal. If there is evidence of gastric erosion, ulcer, or bleeding in any subject confirmed by endoscopy or FOBT, the study will be stopped.

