| Physical Examination | X | update | | | X | | | X |
| Height/Weight | X | Weight only | | | | Weight only | | Weight only |
| 12-Lead ECG ^a | X | | X | X | X | X | | X |
| Vital Signs ^b | X | X | X ^c | X | X | X | | X |
| Serum amylase | X | X | | | X | X | | X |
| Serum lipase | X | X | | | X | X | | X |
| Clinical Chemistry ^d | X | X | | | X | X | | X |
| Hematology ^e | X | X | | | X | X | | X |
| Coagulation ^f | X | X | | | X | X | | X |
| Urinalysis ^g | X | X | | | X | X | | X |
| Monitor urine output ^h | | | X | X | X | | | |
| Infectious Diseases ⁱ | X | | | | | | | |
| SARS-CoV-2 Antigen Test ^j | X | | | | | | | |

| | Outpatient | Inpatient | | | | Outpatient | | Early Termination |
|--|------------|---------------|-----------|-----------|------------------|------------|--------------------------------|-------------------|
| Activity | Screening | Clinic Intake | Treatment | Follow-up | Clinic Discharge | Follow-up | Telephone Contact ^a | |
| Study Day | -30 to -2 | -1 | 1 | 2 | 3 | 7±2 | | |
| Pregnancy Test ^k | X | X | | | | X | | X |
| Birth control methods | X | update | | | update | | update | |
| Sperm, ova, donation and breast feeding check | | X | | | | X | X | |
| FOBT | X | X | | | X | X | | |
| Urine Alcohol & Drug Screen ^l | X | X | | | | | | |
| Prior and Concomitant medications ^m | X | X | X | X | X | X | | X |
| Eligibility Checklist | X | Final check | | | | | | |
| Genetics Tests ⁿ | | X | | | | | | |
| Study Drug Administration | | | X | | | | | |
| Blood Samples for PK ^o | | | X | X | X | | | |
| Adverse Events ^p | | | X | X | X | X | | X |
| Stool Consistency | | X | X | X | X | X | | X |
| Final Subject Disposition | | | | | | X | | X |

^a A 12-lead resting ECG will be obtained at Screening, Day 1 prior to dosing, at 2, 6, 12, 24, and 48 hours post dose, and early termination.

^b Vital signs include sitting (3 minutes) blood pressure, and heart rate, and oral temperature, respiration rate, and pulse oximetry.

^c Blood pressure, and heart rate, respiration rate, and pulse oximetry will be taken pre-dose, then at 15, 30, 60 minutes and 2, 4, 6, 12, 24, and 48 hours post dose. Temperature will be taken pre-dose, 24, and 48 hours post dose. All vital signs will be taken at Day 3 before clinic discharge and Day 7.

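### FOBT is not scheduled at Early Termination, so a dosed subject who leaves before the Day 3 sample can count as not meeting the FOBT stopping criterion without being tested

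*Protocol*

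**What the plan says.** Two protocol sections govern a subject who leaves early. Section 8.10 says that "early termination assessments will be scheduled if the subject agrees, and the assessments in" the schedule of visits will be performed. (The schedule is captioned Table 5 but cited in the text as Table 6.) Section 8.13.1 gives its own list: "a physical examination, body weight, vital signs measurement, ECG, laboratory analyses, Stool Consistency Questionnaire, GI Symptoms Checklist, and AEs will be performed". FOBT is not in that list. In the schedule, in both the protocol and SAP Table 1, the FOBT row is marked at Screening, Day -1, Day 3 and follow-up, and is blank under Early Termination. The study design text agrees on timing: "The FOBT will be performed at screening, clinic intake on Day -1, pre-discharge on Day 3, and at follow-up on Day 7".

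The test has consequences. Under Section 8.13.2 one stopping criterion (b.iiii) is "Any subject has a positive FOBT". Section 11.1.5 adds that, on evidence of erosion, ulceration or "bleeding in any subject confirmed by endoscopy or FOBT, the study will be stopped". The MTD, part of the primary objective, is "the highest dose where no active medication subjects meet the study stopping criteria".

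The GI Signs and Symptoms Checklist (protocol Appendix B), which Section 8.13.1 requires at discontinuation, includes an item on positive FOBT and requires a yes or no. SAP Table 16 tabulates that item at early termination. SAP Table 20, which reports FOBT results, covers Screening, Day -1, discharge and follow-up only, with the categories negative, positive and invalid.

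**The concern.** Local gastric toxicity is the main nonclinical finding (protocol Section 4.9), and FOBT was included because of it (Section 4.7.4). The first post-dose FOBT is on Day 3. A subject who is dosed and leaves before giving that sample has, on the plan as written, no post-dose FOBT.

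Two things follow. First, that subject cannot be distinguished from one who was tested and found negative: the checklist offers only yes or no, Table 20 has neither an early-termination visit nor a not-done category, and SAP Section 9.10 gives no rule for a missing FOBT. Second, the MTD depends on no active subject meeting the stopping criteria, so an untested subject may be counted as not meeting b.iiii for lack of a result. At stake is how much weight the DSMB and the final report can give to a statement that no FOBT was positive at a dose, when only 6 subjects per dose receive active drug.

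**Working it through.** **Is the omission real?** Twelve rows of the schedule are marked at both Day 3 and follow-up: ECG, vital signs, amylase, lipase, chemistry, hematology, coagulation, urinalysis, FOBT, medications, adverse events and stool consistency. Eleven of these are also marked at Early Termination; FOBT is the only exception. The stool consistency row in the SAP shows the contrast: "Stool Consistency | | X | X | X | X | X | | X", where the last mark is Early Termination. Both schedules and the Section 8.13.1 text agree in leaving FOBT out, so this is not a slip in one table.

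**Does the phrase on laboratory analyses cover it?** No. The clinical laboratory table in Section 11.3 does not list FOBT, which has its own schedule row and its own Section 11.7. Section 8.13.1 itself names the two separately among its replacement considerations: "If a subject for some reason is missing safety measures such as clinical laboratory assessments, vital signs, or FOBT".

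**Who is affected?**
- Leaves after dosing, before the Day 3 sample: no scheduled post-dose FOBT.
- Leaves between Day 3 and follow-up: has the Day 3 result, loses the later one.

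**Size.** The inputs are 6 active subjects per dose and true rates p of 10%, 15%, 20% and 25%, both from protocol Section 12.4 and SAP Section 7. The chance of at least one event among n tested subjects is 1 − (1 − p)^n. With n = 6 this reproduces the plan's 47%, 62%, 74% and 82%. I then apply the same formula to a positive FOBT, with one or two active subjects untested.

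| True rate p | n = 6 | n = 5 | n = 4 |
|---|---|---|---|
| 10% | 46.9% | 41.0% | 34.4% |
| 15% | 62.3% | 55.6% | 47.8% |
| 20% | 73.8% | 67.2% | 59.0% |
| 25% | 82.2% | 76.3% | 68.4% |

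For example, at 10% with n = 5: 1 − 0.9^5 = 1 − 0.5905 = 0.4095. One untested subject costs p(1 − p)^5, about 6 to 7 percentage points across these rates.

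The table assumes that FOBT detects every bleed and that leaving is unrelated to bleeding. If those who leave are more likely to bleed, the loss is larger. One or two untested subjects per dose is my illustration; the documents give no early-termination rate.

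**The case against.** The strongest reply is that the gap is narrow and partly covered elsewhere. This is a single-dose study with confinement through Day 3, so having no post-dose FOBT requires leaving the unit within about 48 hours of dosing. Section 11.1.5 lists FOBT among the methods for assessing GI adverse events without tying it to scheduled visits. It also calls for a gastroenterologist's evaluation of reported gastritis or ulcer signs, with endoscopy if judged warranted. Hemoglobin, hematocrit and BUN are measured at early termination, and the required checklist asks about FOBT.

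Much of this stands, and it rules out three stronger readings that a reader might infer.

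- *That an early leaver cannot meet b.iiii.* The criterion counts any positive FOBT, so an unscheduled one would qualify, and the adverse-event criteria and the endoscopy route also stay open.
- *That subjects who leave because of GI symptoms go untested.* They are the ones most likely to be evaluated. The gap is mainly the leaver who reports nothing. Leaving for GI symptoms is plausible, but the documents do not describe it as happening.
- *That replacement biases the gastric result towards safety.* Section 8.13.1 makes non-replacement the default for withdrawn subjects unless the investigator and sponsor agree in writing, and a missing FOBT is only one consideration. A replaced subject who was dosed stays in the safety population (Section 12.2).

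What the reply does not do is produce a result. Unscheduled FOBT and endoscopy are possible but not required, and a replacement supplies another person's test. The checklist records a result without ordering a test: it is also completed on Days 1 and 2, when no FOBT is scheduled.

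**Conclusion.** The point holds as a schedule omission with a reporting consequence. A dosed subject who leaves before the Day 3 sample has no scheduled post-dose FOBT, and the forms and tables would let that subject pass as negative under a criterion that helps define the MTD. With one of 6 active subjects untested, the chance of seeing at least one positive falls from 47% to 41% at a true rate of 10% and from 74% to 67% at 20%, on the assumptions of a perfect test and departure unrelated to bleeding.

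These figures describe what one untested subject would cost. They do not forecast how often it will happen, and one in 6 should not be read as an expected loss. The documents also do not establish a bias of known size or direction. The correction should still be made, because the test bears on the main named risk and the change is small.

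**What to change.** 1. Mark FOBT in the Early Termination column of the protocol schedule and SAP Table 1, and add it to the Section 8.13.1 list, for subjects who have been dosed.
2. If no stool is available at the visit, supply the kit and instructions already used at screening (Section 8.4) and the stamped mailer (Section 11.7), including the dietary and menstrual instructions.
3. Add an early-termination visit and a not-done category to SAP Table 20, and a not-done option to the FOBT item in the checklist and in SAP Table 16.
4. In the cohort report to the DSMB, show any dosed subject without a post-dose FOBT as untested, under the dose received.

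None of this changes a dose or a stopping rule.

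The cost is one FOBT card per early terminator and small edits to the two documents and the checklist. Some cards will not come back, since the visit depends on the subject's agreement; step 3 makes that visible. Samples collected at home have less dietary control than those taken in the unit, where Section 8.6.2 restricts red meat and raw fruit and vegetables. A false positive would count under b.iiii as written, so the collection instructions matter.
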